Accommodative IOLs are designed to expand the range of vision by emulating accommodation. The lens is designed to allow the lens optic to move slightly forward with the contraction of the ciliary muscle. The only accommodative IOL approved in the USA is the Crystalens (Bausch and Lomb). In addition to the non-toric model, there is a toric version (Trulign) that is ideal for patients who also have astigmatism. Different studies have shown limited accommodation (0.25 to 0.75 D), which is not optimal, leading surgeons to target slight residual myopia (-0.50 to -0.75) in the non-dominant eye. Tilting and decentration of the IOL due to contraction and fibrosis of the capsular bag have also been reported.

Multifocal IOLs have evolved since they were initially approved by the FDA in 1997 (Array SA40N, Abbott Medical Optics). Multifocal IOLs (MIOL) have been classified based on their design as refractive or diffractive. Refractive MIOL (i.e ReZoom, Abbot Medical Optics) reportedly provided better intermediate vision compared to a diffractive MIOL (i.e ReSTOR, Alcon Laboratories) that provides better near visual acuity. Mixing and matching these 2 lenses was an option to overcome the limitations that each one presented providing patients with improved intermediate and near acuities. The ReSTOR has been modified while the ReZoom IOL was discontinued 1 - 2 years ago. The original ReSTOR had a +4.0 D add delivering good uncorrected distance and uncorrected near visual acuities (UCDVA and UCNVA) but with limited intermediate acuity with a reading distance of 33 cm. Two new ReSTOR models are currently available in the market, a +3.0 D add to enhance the intermediate distance vision with a reading distance of 40 cm, and a +2.5 D add ideal for people who are interested in distance and intermediate vision (50 - 60 cm) activities. Similarly, to mixing and matching, the use of a ReSTOR +3.0 in one eye and the +2.5 in the fellow eye, known as blended vision, is an option to improve patients' vision at the different distances reducing their dependence on glasses.

Another diffractive MIOL is the Tecnis multifocal (Abbott Medical Optics), with a different design than the ReSTOR, is also available in multiple add powers (+4.0 D, +3.25 D and +2.75 D) to meet the needs and preferences of patients. Patients' complaints of glare and halos are common with all MIOLs. The severity of these symptoms vary according to the actual IOL design.

In July 2016, the FDA approved an extended depth of focus (EDOF) IOL (Tecnis Symfony, Abbott Medical Optics) helping to improve the sharpness of vision at near, intermediate and far distances reducing the need of glasses after cataract surgery. It is available in both a non-toric version and a toric version for patients with astigmatism. The difference between this lens and the multifocal counterpart is that the EDOF, similarly to a monofocal IOL, has one focal point (elongated in the EDOF) while the multifocals have 2 focal points; therefore, having less of a halo and glare problem. Pivotal trial results where Symfony was compared to a monofocal IOL showed similar UCDVA, better intermediate (77% vs. 34% 20/25 UCVA) and near vision (Symfony patients were able to read two additional, progressively smaller lines compared to the monofocal IOL).^A One potential disadvantage of the EDOF IOL compared to a MIOL is the visual performance at near.^B One option to deal with this potential shortcoming is to set the non-dominant eye for a small residual myopic error (-0.50 D)^C what is referred to as nano-vision or mini mono-vision.

The purpose of this study is to evaluate the visual outcomes of an extended depth of focus (EDOF) IOL when both eyes are targeted for emmetropia and when the non-dominant eye is targeted for nano-vision (-0.50 D) with or without astigmatism after routine cataract surgery.

1. OBJECTIVE:

The main objective of this study is to evaluate the visual outcomes of an extended depth of focus (EDOF) toric IOL when both eyes are targeted for emmetropia and when the non-dominant eye is targeted for nano-vision (-0.50 D) in patients undergoing routine cataract surgery.

2. STUDY DESIGN AND METHODS:

2.1. Test article: Toric Tecnis Symfony IOL (ZXT) (Abbott Medical Optics)

2.2. Study Design: Prospective, multicenter (up to 4 sites in USA), randomized, bilateral eye study.

2.3. Subjects:

1. Inclusion Criteria:

Subjects MUST fulfill the following conditions to qualify for enrollment into the trial

1. Subject is undergoing bilateral cataract extraction with intraocular lens implantation.
2. Gender: Males and Females.
3. Age: 40 years and older.
4. Willing and able to provide written informed consent for participation in the study
5. Willing and able to comply with scheduled visits and other study procedures.
6. Scheduled to undergo standard cataract surgery with topical anesthesia in both eyes within 6-15 days between surgeries.

7. Subjects who require an IOL power in the range of +5.0 D to +34.0 D only.
8. Potential postoperative visual acuity of 0.2 logMAR (20/32 Snellen) or better in both eyes.

2. Exclusion Criteria:

Subjects with ANY of the following conditions on the eligibility exam may NOT be enrolled into the trial.

1. Severe preoperative ocular pathology: amblyopia, rubella cataract, proliferative diabetic retinopathy, shallow anterior chamber, macular edema, retinal detachment, aniridia or iris atrophy, uveitis, history of iritis, iris neovascularization, medically uncontrolled glaucoma, microphthalmos or macophthalmos, optic nerve atrophy, macular degeneration (with anticipated best postoperative visual acuity less than 20/30), advanced glaucomatous damage, etc.
2. Uncontrolled diabetes.
3. Use of any systemic or topical drug known to interfere with visual performance.
4. Contact lens use during the active treatment portion of the trial.
5. Any concurrent infectious/non-infectious conjunctivitis, keratitis or uveitis.
6. Clinically significant corneal dystrophy
7. History of chronic intraocular inflammation.
8. History of retinal detachment.
9. Pseudoexfoliation syndrome or any other condition that has the potential to weaken the zonules.
10. Previous intraocular surgery.
11. Previous refractive surgery.
12. Previous keratoplasty
13. Severe dry eye
14. Pupil abnormalities
15. Subject who may reasonably be expected to require a secondary surgical intervention at any time during the study (other than YAG capsulotomy, i.e. LASIK)
16. Anesthesia other than topical anesthesia (i.e. retrobulbar, general, etc).

8. Comatose individuals /traumatized individuals
9. Adults who do not read and/or write
10. Hearing impaired individuals
11. Terminally ill individuals / individuals with life-threatening conditions

3. Study Procedures

3.1. Informed Consent / Subject enrollment

Potential subjects will be identified from the patients presenting at the clinic. Additionally, an ad will be placed in the local newspaper and in the practice website. Once identified as a study candidate, the patient will be asked if he/she would like to participate. The sub-investigator, study coordinator or an appropriately trained staff member will answer any and all questions and will obtain informed consent. A copy of the signed informed consent document will be given to the subject. The principal investigator will be available if the subject wants to discuss further details with him. Any testing that is part of the investigative site's standard preoperative cataract evaluation may be performed prior to the informed consent being signed, provided these tests are conducted within 90 days of surgery. The patient will

understand that participation in the study, or declining to participate, will not affect his/her quality of care.

No subject will be enrolled into the study that does not meet the inclusion/exclusion criteria and does not sign the current approved informed consent document. Informed consent will be obtained prior to collecting any data for the study. The original signed documents will be maintained by the investigator as a permanent part of the subject's research records and a scanned copy will be uploaded to the subject's electronic medical record.

3.2. Surgery Procedures:

Patients will be randomized to one of two groups:

- Group A, plano OU. The target refraction for both eyes will be emmetropia (± 0.25 D).
- Group B, nano-vision. The target refraction for the dominant eye will be plano and for the non-dominant eye -0.50 ± 0.16 D.

3.3. Study Visit Schedule and Assessments (Table 1).

1. Visit Schedule: Subjects will be examined at the following intervals:

1. Visit 1: Screening and enrollment: Preoperative evaluation completed not more than eight weeks before surgery
2. Visit 2: Day of Surgery
3. Visit 3: Day 1: (12 to 48 hours) after surgery
3. Visit 4: Month 1: 30 ± 5 days postoperative after second eye surgery
4. Visit 5: Month 3: 90 ± 15 days postoperative after second eye surgery

3.4. Measurements and evaluations

1. Visit 1: Informed consent process will be conducted at this visit. Assessments include uncorrected and best-corrected ETDRS visual acuity at 4 m (UCVA / BCVA), manifest refraction, intraocular pressure (IOP) using Goldman tonometer, corneal topography, undilated photopic and mesopic pupil size, slit lamp examination including dilated fundus exam, cataract density and type, and HD analyzer. Any testing that is part of the site's standard of care preoperative cataract surgery evaluation may be performed prior to the informed consent being signed provided these tests are conducted within 90 days of the surgery and notation of the date performed is entered onto the CRF. The surgeon's standard pre cataract surgery treatment will be used in all his patients

Each subject will be randomized to Group A or B. Randomization will ensure that an equal number of subjects are enrolled in each group.

2. Visit 2: The surgeon may use his preferred cataract extraction technique (manual or laser). The lens will be implanted in the bag. The following information will be captured the day of surgery: phaco technique (manual or laser), lens implanted and power, target refraction for

IOL power implanted, additional surgical procedures, intraoperative complications, and any device deficiencies. The surgeon's standard post cataract surgery treatment will be used in all his patients. IOL power changes based on intraoperative aberrometry (i.e. ORA) are not allowed but it can be used to align the lens.

3. Visit 3: monocular UCVA, slit lamp examination, IOP, and lens orientation (measured using slit lamp photography).
4. Visit 4: Slit lamp examination, manifest refraction, UCVA, BCVA, UCIVA (at 66 cm), DCIVA (at 66 cm), UCNVA (at 40 cm), DCNVA (at 40), and UCNVA at best distance, undilated photopic and mesopic pupil size, IOP, IOL orientation (measured using slit lamp photography), dilated fundus exam (as deemed necessary by the investigator), patient satisfaction, visual symptoms and spectacle independence questionnaires, HD Analyzer, and any device deficiencies.
5. Visit 5: Slit lamp examination, manifest refraction, UCVA, BCVA, UCIVA (at 66 cm), DCIVA (at 66 cm), UCNVA (at 40 cm) and DCNVA (at 40), and UCNVA at best distance, undilated photopic and mesopic pupil size, IOP, IOL orientation (measured using slit lamp photography), reading speed, defocus curve, dilated fundus exam (as deemed necessary by the investigator), patient satisfaction, visual symptoms and spectacle independence questionnaires, HD Analyzer, keratometry measurement with the device used to calculate the toric power, and any device deficiencies.

All adverse events and complaints will be monitored and recorded at all study visits.

Table 1. Visits and Study Assessments

	Visit 1 Screening	Visit 2 DOS	Visit 3 POD #1	Visit 4 1-Month	Visit 5 3-Month
Informed Consent	X				
Inclusion/Exclusion	X				
Demographics/PMH/Ocular history	X				
UCVA ETDRS (4m)	X		X	X*	X**
Manifest refraction – Max Plus	X			X	X
BCVA ETDRS (4m)	X			X*	X**
UCIVA ETDRS (66 cm)				X*	X**
DCIVA ETDRS (66 cm)				X*	X**
UCNVA ETDRS (40 cm)				X*	X**
DCNVA ETDRS (40 cm)				X*	X**
UCNVA at best distance				X*	X**
Reading speed					X**
Defocus curve					X**

Intraocular Pressure (Goldman)	X		X	X	X
SLE	X		X	X	X
Dilated fundus exam	X			X†	X†
Cataract density / type	X				
Corneal topography	X				
Undilated photopic and mesopic pupil size	X			X	X
Intraop data		X			
Toric IOL position		X	X	X	X
Questionnaires				X	X
HD Analyzer	X			X	X
keratometry measurement with the device used to calculate the toric power					X
AE/Device deficiencies		X	X	X	X

X To be performed as scheduled

* Monocular and binocular testing

** Binocular testing only

† To be performed as deemed necessary by the investigator.

4. Study endpoint criteria

4.1. Patient Completion of Study: If a study patient has completed the final visit (Visit 5) of the study, he/she is considered to have completed the study.

4.2. Patient Discontinuation: Each study patient may voluntarily discontinue the study at any time they choose. Study patients who cannot complete the study for administrative reasons (e.g., non-compliance, failure to meet visit schedule, etc.) will be discontinued from the study. Study patients discontinued during the enrollment phase (prior to surgery) of the study will be replaced.

4.3. Patient Termination: A study patient will be terminated if the study patient develops any severe adverse event that may be related to the study. A study patient will receive appropriate treatment at the discretion of the investigator. Notification of termination will be clearly documented. These study patients are considered to have completed the study and will not be replaced.

4.4. Study Termination: The investigator with appropriate notification may terminate the study. If, after clinical observations, the investigator feels that it may be unwise to continue the study, he may stop the study.

4.5. Study Completion: The study will be complete when all enrolled patients have completed Visit 5 or have been terminated from the study.

5. STATISTICAL CONSIDERATIONS

5.1. Sample size

The sample size estimates depend in large part on the standard deviation (SD) for logMAR UCVA. Assuming a SD of 0.16 (mean from previous Symfony studies)), for the two-sided t-test (alpha =0.05) for the near visual acuity endpoint, we will need 55 subjects in each group (emmetropia / nano-vision) to detect differences of 0.1 logMAR with 90% power. Total sample size = 110. Allowing 10 % for the potential confounding factor of having 4 sites, 120 subjects will be enrolled (60 in each group). Table 2 summarizes the sample size estimate.

Table 2. Sample size estimate.

	Toric Group	
	Emmetropia	Nano-Vision
Sample size	55	55
5% multiple sites	5	5
Total sample size	60	60

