5.2. Statistical Analysis

All data will be collected by the site and entered into a database. Subjects will be assigned an ID number. Data analysis will be performed without patient identification. Statistical analysis will be performed using standard descriptive statistics and other tests as deemed appropriate based on the characteristics of the data to be analyzed. All statistical tests will be two-sided and interpreted at a 5% significance level. Comparisons between the groups will be made. Data analysis will be conducted by a third party consultant.

5.3. Study Endpoints:

Comparisons between the groups:

1. Primary Endpoints:

- Binocular distance-corrected near (40 cm) visual acuity.

- Reduction of astigmatism.

2. Secondary Endpoints:

- Uncorrected and distance-corrected near (40 cm) visual acuity at 1 month and 3 months
- Uncorrected and distance-corrected intermediate (66 cm) visual acuity at 1 month and 3 months
- Uncorrected and best-corrected distance (4 m) visual acuity at 1 month and 3 months
- To evaluate patient's overall satisfaction of their vision
- To evaluate patient's spectacle independence
- To evaluate visual symptoms using a questionnaire.
- Residual mean spherical equivalent refraction at 1 and 3 months
- Residual refractive sphere at 1 month and 3 months
- Residual refractive cylinder at 1 month and 3 months
- Percentage of eyes with postoperative MRSE accuracy to target $\leq 0.5\text{D}$ at 1 and 3 months
- Determine stability of toric iol from time of surgery to 3 months postoperative
- To evaluate the surgeons experience and overall satisfaction

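### Section 5.2 names no model, covariate or site term for near acuity, although the protocol treats site as a possible confounder and answers only by enlarging the sample

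*Combined protocol and SAP*

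**What the plan says.** Section 5.1 sizes the trial "for the two-sided t-test (alpha =0.05) for the near visual acuity endpoint". Its inputs are "Assuming a SD of 0.16 (mean from previous Symfony studies" and a target "to detect differences of 0.1 logMAR with 90% power", which lead to "we will need 55 subjects in each group (emmetropia / nano-vision". It then enlarges the sample because of the sites: "Allowing 10 % for the potential confounding factor of having 4 sites, 120 subjects will be enrolled (60 in each group".

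Section 5.2 sets two-sided testing at the 5% level and says "Comparisons between the groups will be made". Beyond descriptive statistics it leaves the choice of tests to be settled by the nature of the data. It names no model, covariate or site term for near acuity.

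Section 5.3 makes binocular distance-corrected near acuity at 40 cm a primary endpoint and gives no visit for it.

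Section 3.4 and Table 1 show what is recorded at Visit 1: demographics, acuity at 4 m, refraction, topography, cataract density and type, HD Analyzer, and "undilated photopic and mesopic pupil size". Near acuity is not measured before surgery. On allocation, Section 3.4 says "Randomization will ensure that an equal number of subjects are enrolled in each group". Section 8.3 adds that numbered envelopes go to each site. Neither section mentions stratification by site.

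**The concern.** The plan identifies site as a problem and then deals with it in the wrong place. Enrolling more subjects shrinks the standard error. It does not remove between-site variation from the residual, and it does not correct a chance difference in site mix between the groups. A site term in the analysis model does both.

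The same model could carry one or two preoperative values that may be related to near acuity with this type of lens, such as age and pupil size. These are recorded anyway. If they do predict the outcome, the interval for the group difference narrows, and the estimate is protected against chance imbalance between two groups of 60.

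Discretion is also at stake. With no model stated, whether to adjust, and for what, can be decided after the data are seen.

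**Working it through.** **Inputs.** From Section 5.1: SD 0.16, difference 0.1 logMAR, two-sided alpha 0.05, power 90%, 55 per group needed, 60 per group enrolled, up to 4 sites. Allocation is equal (Section 3.4). R, the multiple correlation of the covariates with the outcome within groups, is not in the documents. I assume 0 to 0.4.

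**1. The plan's own figure.** By normal approximation, n = 2(1.960 + 1.282)² × (0.16/0.1)² = 53.8, so 54 per group. With the noncentral t at n = 55, the SE is 0.16 × √(2/55) = 0.0305, the noncentrality is 0.1/0.0305 = 3.28 on 108 df, and power is 90.1%. At 54 per group it is 89.6%. The stated 55 reproduces. At 60 per group the SE is 0.0292, the noncentrality is 3.42 on 118 df, and power is 92.4%.

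**2. Possible gain, ignoring chance imbalance.** The residual SD is 0.16 × √(1 − R²). The noncentral t is used with one df removed for a covariate. The 95% half-width is 1.96 × residual SD × √(2/55).

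| Assumed R | Residual SD | Power at 55 per group | n per group for 90% | Half-width at 55 (logMAR) |
|---|---|---|---|---|
| 0 | 0.160 | 90.1% | 55 | 0.060 |
| 0.2 | 0.157 | 91.2% | 53 | 0.059 |
| 0.3 | 0.153 | 92.6% | 50 | 0.057 |
| 0.4 | 0.147 | 94.3% | 47 | 0.055 |

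The loss of df is trivial: five covariates that predict nothing leave power at 90.1%.

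**3. Possible cost, allowing for chance imbalance.** Covariates differ between groups by chance, and adjusting for them inflates the variance of the group difference. Averaged over randomizations, the factor is about (N − 3)/(N − k − 3), with N subjects in all and k added terms. This is exact for normal covariates and approximate for site indicators. The model proposed here has k = 5: three terms for four sites, plus age and pupil size.

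- N = 120: the factor is 117/112 = 1.045. At R = 0 the noncentrality is 3.42/√1.045 = 3.35 on 113 df, and power is 91.3% against 92.4% unadjusted.
- N = 110: the factor is 107/102 = 1.049. At R = 0 the noncentrality is 3.28/√1.049 = 3.20 on 103 df, and power is 88.7% against 90.1% unadjusted.

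Applying steps 2 and 3 together with k = 5:

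| Assumed R | Power at 55 per group | Power at 60 per group |
|---|---|---|
| 0 | 88.7% | 91.3% |
| 0.2 | 89.9% | just under 92.4% |
| 0.3 | 91.4% | 93.6% |
| 0.4 | 93.3% | 95.2% |
| Unadjusted | 90.1% | 92.4% |

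Break-even is at R of about 0.21 to 0.22. Adding preoperative 4 m best-corrected acuity as a sixth term lowers the R = 0 figure at 60 per group to 91.1%.

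**The case against.** The strongest reply is that the plan has not chosen an unadjusted analysis. The t-test appears only as the basis of the sample size, and Section 5.2 leaves the method open, so an adjusted model is not excluded. Sizing on an unadjusted test and then adjusting is ordinary and usually conservative. This stands. A reader might infer from Section 5.1 that the t-test is the committed primary analysis, but the documents do not say so. The gap is that no analysis is stated.

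The second reply is that the covariates are not shown to be prognostic. This also stands. The documents give no correlation, and the outcome has no baseline value because near acuity is not taken at Visit 1. Best-corrected acuity at 4 m is measured through the cataract that surgery removes, so it may predict little. A reader might infer that the trial is certainly giving up precision. That holds only if R is high enough, and on the figures above a five-term model needs R of about 0.2 to break even.

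The third reply is that the trial meets its power target without adjustment. That is correct on the plan's own assumptions.

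None of this answers the point about site. The protocol raises site as a concern itself, and no analysis step addresses it.

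**Conclusion.** The concern holds as an improvement in method and prespecification. Near acuity has no stated analysis model, and the protocol's own worry about site is met only with 10 extra subjects, which do not adjust for it.

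The size is modest and rests on an assumed R. Ignoring imbalance, the gain at 55 per group is about 1, 2.5 or 4 power points at R of 0.2, 0.3 or 0.4. If the covariates predict nothing, the cost is about 1 point at 60 per group, which still leaves power above 90%. If only 55 per group are analysed and R is 0, power would be about 88.7%, so the covariate list should stay short.

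A reader might take this to mean that 55 per group is wrong or that an unadjusted comparison would be biased. Neither follows. The figure reproduces, and randomization protects the unadjusted comparison from systematic imbalance.

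**What to change.** In Section 5.2, state the primary analysis of binocular distance-corrected near acuity (40 cm), at one named visit, as a linear model with group, site, age and preoperative photopic pupil size. Define pupil size as the mean of the two eyes, because the outcome is binocular. Leave out preoperative 4 m best-corrected acuity, or make it optional and decide before the data are seen. Keep the unadjusted t-test as a sensitivity analysis, and keep 55 per group as the unadjusted basis of the sample size.

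The cost is a sentence or two in Section 5.2 and one model. No new measurement, visit or subject is needed.
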